If candidates encounter an online advertisement, they will be directed to the ONLINE RECRUITMENT QUESTIONNAIRE. If the candidate appears to qualify based on this questionnaire, they will have the opportunity to make a phone screening appointment with the Research Coordinator, during which candidates will be further screened using the IPAQ. Candidates who do not fill out the ONLINE RECRUITMENT QUESTIONNAIRE will be pre-screened by the Research Coordinator over the phone or in person using the PRE-SCREENING PHONE SCRIPT and IPAQ. Subsequently, subjects will be screened in-person following our SCREENING FORM, MEDICAL HISTORY FORM, and CORE TEMPERATURE PILL CONTRAINDICATIONS QUESTIONNAIRE. During this screening, we will assess medical history, BMI, fasting glucose, hemoglobin A1c, and lipid profile to verify eligibility. Further, seated blood pressure will be measured on two separate screening visits to determine resting blood pressure, and in each visit, blood pressure will be measured twice, performed according to clinical guidelines for assessing hypertension⁴. Subjects who undergo the screening and satisfy all inclusion criteria and no exclusion criteria will progress to Protocol 1.

Inclusion criteria: Systolic blood pressure 120-180 mmHg or diastolic blood pressure 80-120 mmHg; ages 35-60.

Exclusion criteria: Hypertensive crisis or target-organ damage; chronic cardiorespiratory or metabolic disease other than hypertension; abnormal resting or exercise ECG (self-reported); currently on antihypertensive drugs; obesity Class 2 or greater (BMI ≥ 35); fasting glucose ≥ 126 ; hemoglobin A1c $\geq 7\%$; LDL ≥ 160 mg/dL; high level of physical activity based on the IPAQ; persons who are pregnant, nursing, or currently trying to conceive. People aged 34 years or younger, or 61 years and older, will not be eligible to participate in the study.

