For Protocol 2, where composite score cognitive function and brain biomarkers of ADRD risk outcomes were not collected at the interim timepoint, separate linear regressions will be performed for each outcome and predictor combination, where the post-intervention timepoint of the measure is the outcome, the pre-intervention measure of the outcome will be included as a covariate, and predictors will be intervention group in Aim 1 and 24H ambulatory systolic and diastolic blood pressure and arterial stiffness measures mean perfusion calibration in gray matter or white matter in Aim 2. Diagnostic plots and Cook's D of linear regressions will be assessed for influential outliers. If found and not improved through transformation, Robust regression using Huber weighting will be utilized instead.

Continuous outcomes will be transformed for normalcy prior to analysis. Methods used to check model assumptions will include checking for extreme outliers by visual inspection and Shapiro test and checking for homogeneity of variance by visual inspection and Levene's test. Full model results will be saved in an appendix or csv file, for possible use in planning future studies, meta-analysis and to enable replication of analysis.

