## 13 Summary of Changes to the Protocol and/or SAP

04/08/2024 updates to the SAP were made to include the analysis plan for Protocol 2 and the Exploratory ANCOVA analysis plan to include corrected definition of acute reductions of post-session supine blood pressure.

04/11/2024 updates to the SAP were made to 1) utilize the memory and list-sorting age-corrected scores rather than percentiles to calculate the Project 2 Aim1 primary outcome composite cognitive score due to their more normal distributions and 2) update the primary efficacy analysis model from mixed effect model to robust linear regression with Huber weighting. Due to there being no interim data collection timepoint for cognitive and MRI measures, pre-intervention values can be included as covariate rather than the more complex approach of including a time x group interaction. Assessment of residual plots indicated potential influential outliers, the impact of which can be mitigated through use of a

robust regression approach.

05/22/24 The SAP was updated to include correlations between pre- to post-intervention in ambulatory and in clinic systolic and diastolic pressure and change from pre- to post first intervention session supine systolic and diastolic blood pressure.

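### Protocol 2's outlier remedy, Huber weighting, limits residuals but not leverage, so in the blood-pressure and perfusion association models one participant can still create or hide an association

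*SAP*

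**What the plan says.** SAP Section 9 fits a separate linear regression for each Protocol 2 outcome and predictor. The post-intervention value is the outcome, and "the pre-intervention measure of the outcome will be included as a covariate". On predictors it states that "predictors will be intervention group in Aim 1 and 24H ambulatory systolic and diastolic blood pressure", and it adds mean perfusion in gray or white matter to the Aim 2 list. Aim 1 therefore has a two-level randomised predictor, and the Aim 2 association models have continuous ones.

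The screen is: "Diagnostic plots and Cook's D of linear regressions will be assessed for influential outliers". The remedy follows: where such points are present and transformation does not help, "Robust regression using Huber weighting will be utilized instead". A later sentence in the section says continuous outcomes will be transformed towards normality. The 04/11/2024 entry in Section 13 gives the reason for choosing Huber: "Assessment of residual plots indicated potential influential outliers, the impact of which can be mitigated through use of a" robust approach.

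The SAP gives no Cook's D cut-off. It specifies no check of hat values, no refit without flagged participants and no estimator that bounds leverage. Section 12 lists no robust-regression package, so the tuning constant is also open. The Protocol caps Protocol 2 at 40 participants (Sections C and D).

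**The concern.** The screen and the remedy measure different things. Cook's D combines residual and leverage. Huber M-estimation reduces a point's weight according to its scaled residual alone. A high-leverage point pulls the fitted line towards itself, so its residual shrinks and it keeps much of its weight. The points with the largest Cook's D can therefore be the ones Huber controls least.

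This matters in the models with a continuous predictor. There, one participant with unusual ambulatory blood pressure or perfusion and a discordant outcome could produce or mask an association with memory or perfusion. Few other safeguards apply: many outcome-predictor pairs are fitted separately, and Section 7.5 makes no adjustment for multiple testing.

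**Working it through.** The plan states no figure to reproduce, and Protocol 2 has no power calculation. The check is by formula and simulation.

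**Inputs.** From the documents: n of at most 40, and the model post ~ pre + one predictor. Assumed: standardised variables, true predictor slope 0, one aberrant participant, and Huber with k = 1.345 and a MAD scale.

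**Formulas.** With p = 3 coefficients, hat value h, least-squares residual e and residual variance s²:

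- Cook's D = e² h / [p s² (1 − h)²]
- Huber weight = min(1, k / |e/scale|)
- A point lying d residual SD off the line fitted without it has a least-squares residual of about d(1 − h).

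The first-step Huber weight is therefore about 1.345 / [d(1 − h)], which rises as leverage rises. For d = 5:

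- h = 0.08: 1.345 / (5 × 0.92) = 0.29
- h = 0.23: 1.345 / (5 × 0.77) = 0.35
- h = 0.43: 1.345 / (5 × 0.57) = 0.47
- h = 0.64: 1.345 / (5 × 0.36) = 0.75

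**Simulation 1** (n = 40, pre-post correlation 0.7, 5-SD residual, 1,000 runs). LS is least squares; rejection is at nominal 5%.

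| SD out on predictor | Mean h | Mean Cook's D | Huber weight | LS slope | Huber slope | Rejection, LS | Rejection, Huber | Rejection, point left out |
|---|---|---|---|---|---|---|---|---|
| 1 | 0.08 | 0.41 | 0.27 | 0.094 | 0.034 | 5.0% | 5.9% | 4.9% |
| 3 | 0.23 | 1.35 | 0.30 | 0.227 | 0.094 | 35.8% | 15.0% | 4.7% |
| 5 | 0.43 | 2.71 | 0.40 | 0.286 | 0.172 | 76.6% | 40.7% | 5.3% |
| 8 | 0.64 | 4.72 | 0.71 | 0.279 | 0.246 | 98.3% | 81.8% | 4.2% |

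As Cook's D rises from 0.41 to 4.72, the Huber weight rises from 0.27 to 0.71. In the first row, an outlier at ordinary leverage, Huber does its job.

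**Simulation 2** (n = 40, post = 0.6 × pre + error, 4-SD residual). False-positive rates from separate runs:

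| Fit | 3 SD out | 4 SD out | 5 SD out |
|---|---|---|---|
| Huber, run 1 (450 data sets) | 13% | 28% | 41% |
| Huber, run 2 (1,000 data sets) | 14% | 26% | 39% |
| Huber, run 3 | 13% | 22% | 41% |
| MM, run 1 | 9% | 22% | 30% |
| MM, run 3 | 10% | 15% | 33% |
| Participant left out | 4–7% | 4–7% | 4–7% |

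In run 1 Huber kept 54%, 64% and 75% of the least-squares bias, and MM kept 14%, 27% and 37%.

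**Milder points.** At 2.5 SD out with a 4-SD residual, Huber rejected in 12% (n = 40). At 3 SD out with a 3-SD residual, two runs gave Huber 14% and 16%. MM gave 17% in the second of these, so it brought no gain there.

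**Hiding an association.** These estimators are regression-equivariant, so the shift caused by the aberrant point does not depend on the true slope. The same shift in the opposite direction masks a real association. At 5 SD out with a 5-SD residual, n = 40, the average shift from the fit without that participant was 1.37 SE with Huber and 0.51 SE with MM.

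**Randomised group contrast.** One baseline 5 SD out with a 5-SD residual shifted the Huber group estimate by 0.34 SE (n = 40) or 0.43 SE (n = 30). The significance verdict changed in 2% and 5% of runs. With baselines 4 to 8 SD out, rejection stayed at about 4.5% to 7%. A separate check gave a Huber bias of about −0.09 with residual SD 0.8. The SE of the contrast is 0.8 × √(1/20 + 1/20) = 0.253, so that bias is 0.09 / 0.253 = 0.36 SE, a similar size.

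**The case against.** The strongest reply is that the SAP does what its own reason requires. Transformation comes first, Huber is the fallback, and Section 13 says the trigger was outliers seen in residual plots, which Huber handles. This stands in part. However, the transformation sentence names outcomes rather than the blood-pressure or perfusion predictors. Residual plots also understate high-leverage points, so they cannot show that leverage was absent.

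Second, the leverage is assumed. The documents give no SD for ambulatory pressure and no probability that one person is extreme on both predictor and outcome. A reader might infer likely leverage from the Protocol's entry range ("Inclusion criteria: Systolic blood pressure 120-180 mmHg or diastolic blood pressure 80-120 mmHg; ages 35-60"). That inference fails. The range applies to seated clinic readings while the predictor is a 24-hour average, and SAP Section 5.2 states a narrower range. Either range curbs extremes without excluding them, and neither limits perfusion.

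Third, a reader might infer that an extreme baseline scan could drive the randomised comparison. The group-contrast results above do not support that.

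Fourth, a reader might conclude that Huber should be replaced by MM. MM lowers bias clearly but error rates only partly, and not at all for a moderate point, so outright replacement is closer to a preference.

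Finally, the SAP claims only mitigation, which Huber does deliver, and Section 7.5 calls the study hypothesis-generating. Both limit the stakes.

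**Conclusion.** The concern holds for the Protocol 2 models with a continuous predictor. Cook's D can flag a leverage point that the written remedy does not control, and no leave-out or leverage-bounding analysis stands beside it. For one participant 3 to 5 SD out with a 4-SD residual at n = 40, Huber false-positive rates are about 13% to 41%, against about 5% without that participant. These sizes depend on assumed scenarios and show what one such participant would do, not how likely one is. Near 2 SD out, Huber rejection was only 6% to 9%. The documents do not support extending the point to the randomised group contrast, or treating Huber as wrong for ordinary residual outliers.

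**What to change.** Keep Huber for residual outliers. Add one sentence to SAP Section 9: for each Protocol 2 model with a continuous predictor, when Cook's D flags a participant, also report (a) the estimate with the flagged participant or participants left out and (b) an MM-estimate, and do not interpret an association that depends on a single participant. State the Cook's D cut-off or, failing that, leave out the participant with the largest value. Name the robust-regression software and tuning constant.

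The cost is a few lines of code and no new data. On clean data MM is about 3% less precise than Huber (SD of the slope 0.141 against 0.137; 0.141 / 0.137 = 1.03). MM reduces the leverage problem at n = 40 without removing it, which is why the leave-out refit is needed as well.

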## 9.1 Exploratory Efficacy Analyses

In addition to Protocol 1 primary analyses, additional exploratory analysis will include analyses of covariance (ANCOVA) for each dependent variable of interest, in which pretest values will be entered as a covariate and treatment condition will be specified as a fixed factor in ANCOVA models. Demographic and physiological variables age, sex, and body mass index will be added one at a time to the ANCOVAs to test for an interaction on treatment effects using the following ANCOVA models with pre-intervention systolic or diastolic blood pressure (Pre SBP, Pre DBP) included as a continuous covariate. ANCOVA models based on the formula Interim or Post BP ~ Pre BP + <Interaction variable> + Intervention + <Interaction variable>\*Intervention and included the following terms in addition to Pre BP: Model 2, Pre BP\*Intervention; Model 3, Age + Age\*Intervention; Model 4, Sex + Sex\*Intervention interaction; Model 5, BMI + BMI\*Intervention interaction. SBP, DBP, age and body mass index (BMI) will all included in models as continuous variables with means estimated at selected values of interaction terms to illustrate how blood pressure measures did or did not vary by subgroup.

For Protocol 1 Aim 3, which is an exploratory aim, analyses of covariance (ANCOVA) models will be used to determine the predictive potential of acute responses for chronic changes in blood pressure. To test the association between acute decreases in blood pressure following an initial heat therapy session or exercise peak test and sustained reduction in resting blood pressures as measured by post-intervention ambulatory blood pressure, we will perform ANCOVA models with pre-session systolic or diastolic blood pressure (Pre-session SBP, Pre-session DBP) included as a continuous covariate. Pre-session BP is an average of three pre-session measurements and Post-session BP is lowest

average of three consecutive readings taken every five minutes in the 55-110 minutes following the hour-long intervention. Group means for ambulatory blood pressure at the post-intervention timepoint will be estimated using the following formulas: Model 1, Post ambulatory BP ~ Pre-session BP + Intervention; Model 2, Post ambulatory BP ~ Pre-session BP + Intervention + Intervention\* Pre-session BP; Model 3, Post ambulatory BP ~ Pre-session BP + Intervention + Post-session BP + Intervention\* Post-session BP. BP measures will be included in models as continuous variables with means estimated at selected values of interaction terms to illustrate how blood pressure measures did or did not vary by subgroup. Additionally, exploratory correlations and PCA were performed among the following Project 1 variables: age, body mass index (BMI), HbA1c, total cholesterol (TC), Interleukin-6 (IL-6), C-reactive Protein (CRP), urine albumin to creatinine ratio (UACR), estimated glomerular filtration rate (eGFR), 24H ambulatory systolic and diastolic blood pressure (Amb. SBP, Amb. DBP), arterial stiffness measure pulse wave velocity (PWV), IPAQ long form continuous score MET-minutes/week (IPAQ), pre-first session resting SBP and DBP, maximum drop in supine SBP or DBP in the 55-110 minutes post-first heat or exercise session (Supine SBP or DBP drop), and total peripheral resistance (TPR), pulse wave velocity (PWV), renin, angiopoietin-2 (Ang2), endothelin-1 (Et1), and urine aldosterone.

In Protocol 2 exploratory analyses, the relationship between outcomes and the highly related covariates/potential confounders listed in **Table 5** at baseline and over time will be characterized through Pearson or Spearman correlations as appropriate based on distributions of data. Clustering of individuals and variables will be characterized through principal component analyses and unsupervised hierarchical clustering. Variables will be centered and scaled prior to principal component analysis. Additional exploratory correlations and PCA were then subsequently performed among the following Project 1 and 2 variables: age, body mass index (BMI), HbA1c, total cholesterol (TC), Interleukin-6 (IL-6), C-reactive Protein (CRP), 24H ambulatory systolic and diastolic blood pressure (Amb. SBP, Amb. DBP), IPAQ long form continuous score MET-minutes/week (IPAQ), pre-first session resting SBP and DBP, mean perfusion calibration of gray matter (Pcalib. GM) and white matter (Pcalib. WM), white matter hyperintensity (WMH) mean and volume, and mean arrival time in gray matter (Arr. Time GM) or white matter (Arr. Time WM), cognitive measure mini-mental state exam (MMSE, measured at pre-intervention only), list age-corrected sorting score and age-corrected picture sequence score, memory domain composite score (memory score, average z-scores of list age-corrected sorting score and age-corrected picture sequence score) and brain biomarkers of ADRD risk, whole hippocampus, right and left entorhinal cortex normalized to estimated total intracranial volume (LERC/eTIV, RERC/eTIV).

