Exercise Training. For Exercise Training sessions (Exercise Training group only), subjects will report to the lab for a supervised exercise training session 3-4 times per week. Subjects will be instrumented with a heart rate monitor chest strap and heart rate will be constantly monitored during training sessions. During the first and final session of Exercise Training for each subject, core temperature will be continuously monitored and recorded using a wireless, disposable core temperature sensing pill. Exercise will consist of a 5-minute warm-up of seated upright cycling at 30% of the subject's VO_2 peak, followed by 40 minutes of cycling at 60% VO_2 peak, then a 5-minute cool down at 30%. There are some risks associated with exercise, including: light-headedness, fatigue, muscle cramps, and shortness of breath. Procedures will be terminated immediately if any subject feels light-headed, nauseated, or experiences any other adverse signs or symptoms.

1st Heat Therapy or Exercise Training Session. During the 1st heat therapy or exercise training session, we will measure the acute post-heating/exercise hypotension response. This information will be used to test the predictive power of acute post-heat/exercise hypotension on the individual response to the interventions. The subject will lay supine for 20 min of rest followed by three measures of blood pressure before the heat therapy or exercise training session. At the end of this 1st session, the subject will lay down for 1 hour of recovery, during which we will continue to monitor core temperature, heart rate, and blood pressure every 5 min.

Protocol 2:

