## 4 Study Objectives and Endpoints

### 4.1 Study Objectives

#### Protocol 1

**Specific Aim 1:** Utilizing a prospective randomized clinical trial study design, we will determine whether heat therapy improves **blood pressure** (both in clinic and ambulatory) better than dynamic aerobic exercise, the gold-standard non-pharmacological treatment of essential HTN. Specifically, we hypothesize that 30 sessions of passive heat therapy using hot water immersion over 8-10 weeks will improve blood pressure in HTN individuals to a greater extent than 30 sessions of exercise training over the same time period.

**Specific Aim 2:** We will determine whether heat therapy will improve biomarkers of arterial health and compare responses to exercise training. We hypothesize that 30 sessions of heat therapy will improve arterial stiffness in HTN to a greater extent than exercise. Furthermore, we hypothesize key clinical biomarkers of systemic inflammation and oxidative stress will be improved following heat therapy.

**Specific Aim 3:** In an exploratory aim, we will determine whether the acute decreases in blood pressure following an initial heat therapy session or exercise peak test predict the sustained reduction in resting blood pressures following heat therapy treatment or exercise training in HTN. These findings would provide significant predictive information beyond baseline resting blood pressures. We hypothesize that the reduction in blood pressure following acute stressors will be predictive of treatment effects on resting blood pressure.

#### Protocol 2

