**HEAT THERAPY VS EXERCISE TRAINING IN HYPERTENSION SAP**

dbp_dipper	Aim 1/Secondary	Categorical; non-dipper <10%, dipper ≥10% to <20%, and extreme dipper ≥20% change in diastolic BP at night calculated from ambulatory BP day and night averages
pwv	Aim 2/Primary	Continuous; average of three pulse wave velocity measurements collected at pre-, interim-, and post-intervention timepoints
il6_lg2	Aim 2/Secondary	Continuous; Biomarker IL-6 with the lower limit of detection (LLD) of 0.031 imputed for <LLD, log2 transformed for normalcy
crp_lg2	Aim 2/Secondary	Continuous; Biomarker CRP with the lower limit of detection (LLD) of 0.031 and upper LD (ULD) of 50 imputed for <LLD and >ULD, log2 transformed for normalcy
et1_lg2	Aim 2/Secondary	Continuous; Biomarker ET-1 with the lower limit of detection (LLD) of 0.031 imputed for <LLD, log2 transformed for normalcy
alb_lg2	Aim 2/Secondary	Continuous; Biomarker urine albumin with the lower limit of detection (LLD) of 0.031 imputed for <LLD, log2 transformed for normalcy
Supine.SBP.low	Aim 3/Primary	Continuous; average of three lowest consecutive supine systolic blood pressure measurements taken every 5 minutes for an hour post-intervention during supine recovery (for Heat Therapy: syst_bp55_ht_s1 to syst_bp110_ht_s1; for Exercise Training: for Heat Therapy: syst_bp55_ex_s1 to syst_bp110_ex_s1)
Supine.DBP.low	Aim 3/Primary	Continuous; average of three lowest consecutive supine systolic blood pressure measurements taken every 5 minutes for an hour post-intervention during supine recovery (for Heat Therapy: syst_bp55_ht_s1 to syst_bp110_ht_s1; for Exercise Training: for Heat Therapy: diast_bp55_ex_s1 to diast_bp110_ex_s1)
Supine.SBP.1.ch	Aim 3/Primary	Change from average pre-session resting SBP to Supine.SBP.low
Supine.DBP.1.ch	Aim 3/Primary	Change from average pre-session resting DBP to Supine.SBP.low
eGFR	Aim 1/Exploratory	eGFR was calculated using the CKD-EPI Creatinine-Cystatin Equation (2021) using the CKDEpi_RF.creat.cys function in the nephron R package and rounded to two decimal places
uacr	Aim 1/Exploratory	Urine albumin creatinine ratio (mg/g) was calculated by dividing urine albumin by urine creatinine/1000 rounded to 2 decimal places
Protocol 2		
cognitive_score	cognitive/Primary	Averaged z-scores (centered & divided by standard deviation) of age-corrected picture sequence score (age_cor_score)

		and age-corrected list-sorting score (list_age_cor_scpre)
--	--	--

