## 9 Efficacy Analyses

For primary analyses for Protocol 1 Aims 1, primary outcomes will be compared between groups (heat therapy vs exercise training) over time (within subject repeated measurements) using two-way repeated measures mixed model including an interaction between intervention group and timepoint with pre-defined contrasts. For Specific Aim 1, to test the hypothesis that heat therapy improves blood pressure (both in clinic and 24H ambulatory) better than dynamic aerobic exercise, the null hypothesis will be that the interaction between group and timepoint is equal to 0. For Aim 2, to determine whether heat therapy will improve biomarkers of arterial health (arterial stiffness & biomarkers of systemic

inflammation and oxidative stress) and compare responses to exercise training, the null hypothesis will be that the interaction between intervention group and timepoint is equal to 0. For Aims 1 and 2 exploratory analyses, ANCOVA will be performed for primary and secondary outcomes, with pretest values entered as a covariate and treatment condition specified as a fixed factor. Demographic and physiological variables (age, sex, BMI) and pre-intervention blood pressure will be added one at a time to the ANCOVAs to test for an interaction on treatment effects. For Aim 3, we will use ANCOVA models to determine the predictive potential of acute post-exercise hypotension response for chronic changes in blood pressure, with pretest values entered as a covariate and systolic and diastolic blood pressure specified as a fixed factor. Analyses will be performed on the Intention to Treat population. Additionally, change from pre- to post-intervention in ambulatory and in clinic systolic and diastolic pressure will be correlated with change from pre- to post first intervention session supine systolic and diastolic blood pressure by Pearson correlation.

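### The adjusted Aim 3 models use only ambulatory pressure and omit its baseline, so prediction of resting blood pressure beyond its baseline rests on an unadjusted correlation

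*SAP*

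**What the plan says.** **The aim.** Protocol section B and SAP 4.1 state Aim 3 in the same words: whether "acute decreases in blood pressure following an initial heat therapy session or exercise peak test predict the sustained reduction in resting blood pressures". Both add that the result should give predictive information beyond baseline resting pressure. The hypothesis is that the "reduction in blood pressure following acute stressors will be predictive of treatment effects on resting blood pressure". SAP Table 1 lists the Aim 3 outcome only as acute and chronic pressure reductions, without naming the measure.

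**The ANCOVAs.** SAP 9.1 takes the outcome to be "sustained reduction in resting blood pressures as measured by post-intervention ambulatory blood pressure". The formulas begin with "Model 1, Post ambulatory BP ~ Pre-session BP + Intervention". Model 2 adds the interaction of intervention with pre-session pressure. The third is "Model 3, Post ambulatory BP ~ Pre-session BP + Intervention + Post-session BP" plus the interaction of intervention with post-session pressure.

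**The covariates.** SAP 7.3 lists pre-intervention 24-hour ambulatory pressure and the pre-session average as separate covariates for section 9.1. SAP 9 says that the Aim 3 ANCOVAs enter pretest values as a covariate.

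**The correlation.** SAP 9 adds that "change from pre- to post-intervention in ambulatory and in clinic systolic and diastolic pressure will be correlated with" the supine change at the first session. The change log dates this addition to 05/22/24.

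**The acute measurement.** Protocol section C, under the 1st Heat Therapy or Exercise Training Session, says: "During the 1st heat therapy or exercise training session, we will measure the acute post-heating/exercise hypotension response". SAP Table 4 derives the acute variable from session-1 fields, as "Change from average pre-session resting SBP to Supine.SBP.low".

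**The concern.** The aim names one quantity and the adjusted models use another. The SAP treats clinic and ambulatory pressure as different measures. Clinic pressure is the mean of three readings (Table 3). Ambulatory pressure is a weighted 24-hour average over waking and sleeping hours (section 5.5 and Table 4). They are listed separately among the Aim 1 primary outcomes.

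The response is also a level measured after treatment, with no adjustment for where that same measure began. As printed, the models do not estimate a reduction in ambulatory pressure. People with a higher ambulatory pressure at entry will tend to have a higher one at the end. If the post-session reading carries information about that starting level which the pre-session reading lacks, it can look predictive without predicting any change.

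At stake is what an Aim 3 result can be said to show. The aim's added value is prediction beyond baseline, and no planned analysis delivers that for resting pressure.

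**Working it through.** The documents give no sample size or power for Aim 3, so there is no stated figure to reproduce. The first check compares the planned analyses with the aim.

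| Analysis | Response | Acute-response term | Baseline of the response | Group term |
|---|---|---|---|---|
| Model 1 (SAP 9.1) | Post ambulatory level | No | No | Yes |
| Model 2 (SAP 9.1) | Post ambulatory level | No | No | Yes |
| Model 3 (SAP 9.1) | Post ambulatory level | Yes | No | Yes |
| Pearson correlation (SAP 9) | Change in ambulatory and in clinic pressure | Yes | Only through the change score | No |

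Three things follow.

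1. Models 1 and 2 cannot address Aim 3 whatever the response, because neither contains the acute response. They serve at most as comparators for Model 3.
2. Clinic pressure meets the acute response only in the last row. That correlation pools the arms and does not condition on baseline pressure, so it cannot separate prediction by the acute fall from prediction by the starting level.
3. SAP 15 lists no Aim 3 table or figure, so sections 9 and 9.1 are the only specification of the analysis.

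**Does the missing baseline term matter?** Model 3 was simulated with no true link between the acute response and the change in ambulatory pressure. There were 40 participants (the Protocol's planned completers), equal arms and 4,000 runs per scenario, tested at two-sided 0.05. The test was on the post-session term, averaged over arms. The following are assumptions, not figures from the documents: a correlation of 0.7 between baseline and post-intervention ambulatory pressure, and the three correlations in the table. Write A for baseline ambulatory, P for pre-session and Q for post-session pressure. The bias depends on the partial correlation of A with Q given P:

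(r_AQ − r_AP × r_PQ) / √[(1 − r_AP²)(1 − r_PQ²)]

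For the third row this is (0.60 − 0.60 × 0.70) / √(0.64 × 0.51) = 0.18 / 0.571 = 0.32.

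| r_AP | r_AQ | r_PQ | Partial correlation | Rejection rate, Model 3 as printed | Rejection rate with baseline ambulatory added |
|---|---|---|---|---|---|
| 0.60 | 0.42 | 0.70 | 0 | 5.0% | 4.8% |
| 0.60 | 0.50 | 0.70 | 0.14 | 7.8% | 5.3% |
| 0.60 | 0.60 | 0.70 | 0.32 | 20.7% | 5.4% |
| 0.50 | 0.50 | 0.60 | 0.29 | 19.6% | 5.3% |
| 0.70 | 0.70 | 0.80 | 0.33 | 19.3% | 5.0% |

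The simulation error at a 5% rate is √(0.05 × 0.95 / 4000), about 0.3 percentage points. The printed model is sound when pre-session pressure carries all that post-session pressure knows about baseline ambulatory pressure (first row). Otherwise it can find an association where the acute fall predicts no change. Adding the baseline restores the nominal rate in every scenario tried.

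**Cost of the extra term.** Model 3 has five coefficients: intercept, pre-session, intervention, post-session and interaction. With 40 completers the residual degrees of freedom go from 40 − 5 = 35 to 40 − 6 = 34.

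**The case against.** A reader might infer that the Aim 3 hypothesis is not tested at all. The documents do not support that. The correlation in SAP 9 sets the first-session fall against the change in clinic pressure, and it was added deliberately. What is missing is the adjusted version.

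A reader might also infer that a real association with resting pressure would be missed for want of power. That does not follow. The planned clinic correlation keeps whatever power that comparison has, and the documents give no correlation between clinic and ambulatory changes from which to compute a loss.

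The choice of ambulatory pressure is open and has a rationale. SAP 9.1 states it in the text and in every formula, and the Protocol's section on ambulatory monitoring cites its generally better prognostic value than office pressure. This stands as a reason to keep the ambulatory model. It does not make a 24-hour average a resting pressure.

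Pre-session pressure is itself a supine resting reading, so Model 3 does adjust for one resting baseline. It is still not the baseline of the response. SAP 7.3 lists the two separately, though for section 9.1 as a whole, so the omission from the formulas may be an oversight.

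Finally, the reference to a peak exercise test might suggest that a finding in the exercise arm would be credited to the wrong stimulus. The plan leaves little room for that. The recovery readings are scheduled at the first session, the derived fields come from session 1, and the VO₂ peak description includes no recovery pressure series. The hypothesis sentence speaks only of acute stressors, and the heat-arm wording already matches. This is a wording correction.

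**Conclusion.** The point holds in limited form and is minor. The comparison of aim, formulas and correlation rests on the text alone and needs no assumption. The adjusted Aim 3 analysis addresses ambulatory pressure only and does not condition on its baseline, while resting pressure gets only an unadjusted correlation.

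The practical size of the missing baseline term cannot be fixed from the documents. Under the assumed correlations, the false-positive rate for the post-session term ran from 5% to 21%, against about 5% with the baseline included. This range shows what could happen and does not forecast this trial.

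Aim 3 is labelled exploratory, and SAP 7.5 describes the study as focused on learning and hypothesis generation. No primary blood-pressure conclusion depends on this analysis.

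**What to change.** 1. In SAP 9.1, fit Model 3 also with post-intervention clinic systolic and diastolic pressure (syst_bp_mean, diast_bp_mean) as responses, with the matching pre-intervention clinic value as covariate. Name the pre-test visit as its source, since SAP 8.1 uses the same variable names at screening.
2. Keep the ambulatory Model 3 and add pre-intervention ambulatory pressure of the same type (systolic or diastolic). This brings the formula into line with SAP 7.3 and 9.
3. Do not refit Models 1 and 2 on clinic pressure as tests of Aim 3, since they contain no acute-response term.
4. Reconcile the peak-test wording in Protocol section B, SAP 4.1 and SAP 9.1 with the first training session, at which the recovery readings are taken.

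The clinic readings are already collected before, midway through and after the intervention, so no new data are needed. The cost is two more Model 3 fits (systolic and diastolic), hence one more exploratory outcome to report in a plan without multiplicity control, and one extra term at about 40 completers.
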